#### **8.4 Criteria for Discontinuation or Withdrawal of a Subject**

The primary reason for discontinuation or withdrawal of the subject from the study should be noted using the following categories. For screen failure subjects, refer to Section 9.4.2.

1. Lost to follow-up. The subject did not return to the clinic and at least three attempts to contact the subject were unsuccessful. All attempts to contact the subject must be documented.
2. Voluntary withdrawal. The subject wishes to withdraw from the study. The reason for withdrawal, if provided, should be recorded in the eCRF. NOTE: All attempts should be made to determine the underlying reason for the withdrawal and, where possible, the primary underlying reason should be recorded).
3. Study termination. The sponsor, Independent Ethic Committee (IEC), or regulatory agency terminates the study.
4. Other. NOTE: The specific reasons should be recorded in the eCRF.

#### **8.5 Procedure for Discontinuation or Withdrawal of a Subject**

A subject may discontinue his or her participation without giving a reason at any time during the study. Should a subject's participation be discontinued, the primary reason for termination must be recorded in the eCRF. In addition, efforts should be made to perform all procedures scheduled for the Month 6, 12 and 18 visit if discontinuation is prior to that visit, or the Month 24 visit if discontinuation is after Month 18 but before Month 24. Discontinued or withdrawn subjects will not be replaced.

#### **8.6 Subject Follow- up after trial completion or early termination**

After completion of the last study visit the subject will continue to participate in the site specific VAD Follow- up program and may have the possibility to be included in a registry or follow- up trial.

## **9.0 STUDY PROCEDURES, DEVICE EXPLANT AND STUDY EVALUATIONS**

### **9.1 Study Procedures**

The following sections describe the procedures to be completed throughout the conduct of the study. Subjects are to be assessed by the same investigator or site personnel whenever possible. The Schedule of Study Procedures is described here in Section 9 and also in Appendices 17.1.1 and 17.1.2. Every attempt should be made to perform evaluations at the designated time points. However, for visits conducted at Month 1, 3 there is a window of  $\pm 7$  days for visits at Month 6, 24 there is a window of + 14 days and for visits at Month 12, 18 there is a window of - 14 days.

#### **9.1.1 Informed Consent Procedure**

Before enrolling the subject in the trial, i.e., before any trial-related examination is performed, a written ICF must be obtained. Each potential participant shall be informed of the aim of the trial and what participation entails. They shall be supplied with an Information Sheet summarizing the details of the trial. Ample time should be given to the subjects to consider their participation. Agreement to participate in the trial is to be confirmed by the subject and the principal investigator (or authorized designee) by signing and dating the consent form. Documentation of this procedure is required in the medical record.

Standard of care assessments obtained within the 30 days prior to consent for screening may be used: 1) to confirm eligibility; and 2) for screening measurements, if the subject meets eligibility criteria and signs the ICF. Echocardiograms obtained within the 6 months prior to ICF may be used for screening measurements.

Vulnerable populations will not be included in this trial.

#### **9.1.2 Point of contact**

A point of contact of where to obtain additional information on the trial, on the rights of the subject and whom to contact in the event of trial-related injury will be provided to each subject. This information will be specified in the ICF.

#### **9.1.3 Informing the subject's general practitioner**

In certain applicable countries, and in cases where the subject is typically treated by a general practitioner or other equivalent health care provider, then with the subject's agreement this health care provider is to be informed of the subject's participation in the trial at enrollment. The provider should be informed of the title of the trial, date of enrollment into the trial, and the dates of the outstanding visits. The communication with the general practitioner should be documented in the subject's medical record.

## 9.1.4 Demographics, Medical History, and Physical Examination

### 9.1.4.1 Demography

Demographic data that will be collected and identified by a non-identifying number on the eCRF include sex, year of birth, gender, weight, height, race and ethnicity\*. Subject BMI and BSA will also be recorded.

\* per country specific regulation

### 9.1.4.2 Cardiovascular/ Medical history & Hospitalization

Medical history will be collected and recorded for all subjects enrolled in the trial. This includes diagnosis, general medical history and cardiovascular history as follows:

- General medical history
- Primary cardiac diagnosis
- Previous cardiac surgery
- Current mechanical support (ECMO, balloon pump)
- Previous mechanical circulation support
- Etiology of Heart Failure
- Duration of Heart Failure
- Number of hospitalizations in past year for cardiac
- Smoking

With co-morbidities to be identified as

- Diabetes (diet, oral, insulin)
- COPD
- Previous neurological event
- Carotid artery disease
- Peripheral vascular disease
- Arterial Fibrillation
- NYHA class

Childhood illnesses, unless considered to be relevant to the etiology of heart failure, do not need to be documented.

**9.1.5 Hemodynamic parameters/ Vital Signs & Improved Blood Pressure Management Plan (IBPM)****9.1.5.1 Hemodynamic parameters/ Vital Signs**

Hemodynamic parameters will include the following, which will be captured at screening/ pre-implant, day 1-3, and month 1, 3, 6, 12, 18, 24, and re-hospitalization (where applicable):

	Screening	Day 1-3 post implant	Month 1, 3, 6, 12, 18, 24
Heart Rate/ Rhythm	x	x	x
Respiratory Rate	x	x	x
Temperature	x	x	x
Systolic blood pressure	x	x	x 
Diastolic blood pressure	x	x	x 
Mean Arterial Blood Pressure (MAP) 	x	x	x 
Doppler - Pressure	x	x	x 
Central venous pressure 	x		
SVO 2	x	x*	x*
Right atrial pressure 	x		
Systolic pulmonary artery pressure 	x		
Diastolic pulmonary artery pressure 	x		
Mean pulmonary artery pressure 	x		
PCWP	x		
Cardiac Index	x		
Cardiac output	x		
PVR 	x		

\*if available

 follow IBPM program (Section 9.1.5.2) as applicable

 After screening only to be collected in case of late Right Heart Failure

 Auto calculated Every effort should be made to obtain hemodynamic assessments per the Time and Event Schedules (Appendix 17.1.1). However, some parameters are available only during right heart catheterization (RHC) monitoring, while others are not available due to RHC monitoring. In addition, some parameters may not be available in some subjects who have a VAD implanted. A hemodynamic parameter that is not available due to RHC monitoring or implant status is not considered to be protocol deviation. However, the ability/inability to obtain hemodynamics due to presence of a RHC will be documented in the eCRF, as needed.

### 9.1.5.2 IBPM, Mean Arterial Blood Pressure (MAP) Assessment Procedure and Documentation

#### General

From the Instructions For Use (IFU), the recommended MAP target for subjects supported by the MVAD System is  $\leq 85$  mmHg (as tolerated) for subjects using an automated cuff method and  $\leq 90$  mm Hg for subjects who use the Doppler/cuff method.

While both device approaches yield MAP values within approximately 5 mm Hg of arterial line measurements, the Doppler/cuff method appears to give slightly higher values in non-pulsatile patients and a small adjustment is provided.

Following discharge from the index hospitalization, all subjects are required to adhere to an IBPM plan, in addition to receiving standard follow up care. Prior to discharge, subjects/caregivers will be trained to take blood pressures and record values (Automated cuff or cuff/Doppler) in a Blood Pressure (BP) diary.

Following discharge, the blood pressure will be obtained twice a day for at least the first 3 months and continue until the subject is medically stable with blood pressure within the recommended values (defined as MAP measurements  $\leq 85/90$  mmHg) and as medically appropriate for the subject.

Stability (defined as MAP measurements  $\leq 85/90$  mmHg) and compliance with the IBPM plan will be assessed by HeartWare based on Time in Therapeutic Range analysis (TTR) at monthly intervals for the first 3 months post-discharge, although it is understood that blood pressure is volatile and continuous monitoring is an essential element of improved blood pressure management.

After continuous monitoring for the first 3 months post initial discharge regardless of re-hospitalizations, stable subjects will have quarterly (3 month) TTRs performed to assess compliance. For subjects who have not met the stability definition, monthly monitoring will continue for another 3 month period. This will be repeated as often as necessary until subjects are stable.

All blood pressure measurements, including those recorded in the patient diary as well as any intervention such as medication changes to maintain the blood pressure within the therapeutically recommended ranges will be documented in the eCRF.

#### Method of Measurement

HeartWare will provide a blood pressure cuff and Doppler device for all enrolled MVAD subjects. It is anticipated that cuffs of different sizes will be required and a selection of cuffs of different size will be provided to sites.

The protocol for blood pressure measurements is similar to that currently used in the current HeartWare US ENDURANCE Supplemental Trial. It is simple, reproducible and requires only that subjects be divided into 2 groups: those that have a palpable radial pulse and those who do not. For subjects with a palpable radial pulse, a standard

method of blood pressure measurement will be employed, namely an automated cuff. The specific methodology is listed below:

1. If the subject has a palpable radial pulse (approximately 40% of subjects), a Blood Pressure Cuff (BPC) will be used to obtain blood pressure measurements (systolic and diastolic) and MAP calculated as follows:  
$$\text{MAP} = (\text{Systolic Blood Pressure} + [2 \times \text{Diastolic Blood Pressure}]) / 3$$
2. If the subject has no palpable radial pulse, a Doppler and BPC will be used and the opening pressure will be reported as MAP.

Measurement of mean arterial pressure is the goal and it is understood that cuff/Doppler pressures are expected to be 5 – 8 mm Hg higher than MAP measured by the automated cuff method. To adjust for this difference, the upper limit for MAP will be set at  $\leq 90$  mm Hg for cuff/Doppler subjects.

Sites will input raw blood pressure data (systolic, diastolic or Doppler pressures) into the eCRF and automated calculations will be performed within the database.

### **Index Hospitalization**

All subjects will be provided with a blood pressure monitoring device (Doppler and blood pressure cuff, if blood pressure cannot be measured with a cuff alone) at implant. As soon as subjects are ambulatory, training will begin on blood pressure devices.

### **Prior to Discharge**

Subjects implanted with the MVAD pump and caregivers must demonstrate competence to take accurate blood pressure measurements. Subjects/caregivers will be educated about the specific blood pressure values that are within the target range and will also be provided with instructions regarding out-of-range blood pressure values and when to contact the Investigator/Site VAD Team (see below). The subjects and caregivers training and competency will be documented as in Appendix 17.8.3 and 17.8.4 and in the eCRF.

A patient diary will be provided to the subject, along with the Investigator/Site Team contact information.

### **After Discharge**

Specific instructions will be given to maintain MAP  $\leq 85/90$  mm Hg throughout the trial. At discharge, all subjects will be provided with a blood pressure cuff and Doppler device. Both the subject and caregiver will be trained on the use of the cuff and the cuff/Doppler combination. It is required to record blood pressure twice daily (time of day may be chosen by subject but must be done consistently) in the diary, starting the day after discharge. For subjects who have a radial pulse, systolic and diastolic blood pressures will be obtained. For subjects who do not have a radial pulse, the Doppler opening pressure will be obtained. The blood pressure data will be submitted weekly to

the site via FAX, email or telephone for the duration of the IBPM and subjects must immediately report any of the following for medical advice:

1. A *cuff systolic* reading exceeds 130 mm Hg or *cuff diastolic* exceeds 95 mm Hg on 2 successive days. If this happens, the subject or caregiver will notify the site immediately.
2. For cuff/Doppler readings, if the opening pressure (MAP) exceeds 100 mm Hg on 2 successive days, the subject or caregiver will notify the site immediately.
3. A MAP of  $\leq 60$  or systolic BP of  $\leq 100$  with clinical symptoms of hypotension (dizzy, orthostasis, etc.) will trigger notification of the site with subsequent adjustment of medications.

All blood pressure measurements recorded in the diary will be entered into the database within 48 hours of receipt of the patient diary. When stable after the first 3 months, blood pressure measurements may be obtained during regular VAD clinic visits.

For subjects/caregivers who are unable to obtain reliable MAP measurements, the subject needs to return to the site on a regular basis.

The blood pressure measurements must be recorded in the patient diary regardless of the discharge facility (home, rehabilitation or other health care facilities), or re-hospitalizations due to adverse events, for at least the first 3 months post initial discharge.

It is recommended that each study center document their study IBPM data collection procedures and their implementation.

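### A small corner of cuff readings with mean arterial pressure above 100 mmHg needs no immediate report, although Doppler subjects must report above 100 (low priority, patient safety)

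*Protocol*

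**What the plan says.** Protocol 9.1.5.2 manages blood pressure by MAP in both measurement groups, with a target of at most 85 mmHg by automated cuff and at most 90 mmHg by Doppler with cuff. The subsection Method of Measurement gives the reason for the two figures: Doppler is expected to read 5-8 mmHg higher. It applies the adjustment to the target: "To adjust for this difference, the upper limit for MAP will be set at" 90 mmHg or less for Doppler subjects.

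The subsection After Discharge lists what must be reported at once.

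- Item 1, cuff subjects: "A *cuff systolic* reading exceeds 130 mm Hg or *cuff diastolic* exceeds 95 mm Hg on 2 successive days".
- Item 2, Doppler subjects: "if the opening pressure (MAP) exceeds 100 mm Hg on 2 successive days".
- Item 3, low pressure with symptoms: MAP of 60 or less, or systolic of 100 or less.

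Cuff subjects do not record a MAP: "For subjects who have a radial pulse, systolic and diastolic blood pressures will be obtained". Sites put the raw values "into the eCRF and automated calculations will be performed within the database". As to routine flow, "The blood pressure data will be submitted weekly to" the site, and diary values "will be entered into the database within 48 hours of receipt of the patient diary". The scheme relaxes later: "When stable after the first 3 months, blood pressure measurements may be obtained during regular VAD clinic visits".

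**The concern.** The controlled quantity is MAP, but only the Doppler group has a high-pressure call-in rule stated in MAP. Item 2 does not extend to cuff-only readings, because the General part of 9.1.5.2 treats the automated cuff and the cuff/Doppler combination as separate methods. If the systolic and diastolic limits let through readings whose MAP exceeds 100, a cuff subject could be above the level at which a Doppler subject must phone, on the same 2 successive days, with nothing in the list telling that subject to phone. What is at stake is the time until the site sees a high reading in a home-monitored subject with a first-in-human pump, mainly in the first 3 months or until pressure is stable.

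**Working it through.** The plan states no MAP equivalent for the cuff limits, so there is no figure to reproduce. The check derives one.

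**Inputs (all Protocol 9.1.5.2).** Cuff MAP = (SBP + 2 × DBP)/3. Cuff call-in: SBP above 130 or DBP above 95. Doppler call-in: MAP above 100. Both need 2 successive days. Doppler minus cuff: 5 to 8 mmHg.

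**Step 1: highest MAP that triggers nothing.** Let PP = SBP − DBP. Then MAP = DBP + PP/3 = SBP − 2PP/3. A reading that triggers nothing has SBP ≤ 130 and DBP ≤ 95, so its highest MAP is

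- 95 + PP/3 for PP up to 35, where the diastolic limit binds;
- 130 − 2PP/3 for PP above 35, where the systolic limit binds.

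**Step 2: where this exceeds 100.** 95 + PP/3 = 100 gives PP = 15. 130 − 2PP/3 = 100 gives PP = 45. The gap exists only for PP strictly between 15 and 45.

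| PP (mmHg) | Highest reading with no trigger | MAP (mmHg) |
|---|---|---|
| 15 | 110/95 | 100.0 |
| 20 | 115/95 | 101.7 |
| 25 | 120/95 | 103.3 |
| 30 | 125/95 | 105.0 |
| 35 | 130/95 | 106.7 |
| 40 | 130/90 | 103.3 |
| 45 | 130/85 | 100.0 |

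The peak is 320/3 = 106.7, which is 6.7 above the Doppler call-in level. The region is a triangle with corners 130/85, 130/95 and 110/95. Listing all whole-number readings gives 110 pairs inside it, at PP 16 to 44. Examples: 125/92 gives 309/3 = 103.0; 128/90 gives 308/3 = 102.7; 120/92 gives 304/3 = 101.3.

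**Step 3: direction of the method difference.** Adding the expected 5-8 mmHg, a cuff MAP of 103 corresponds to a Doppler reading of about 108 to 111. The difference between methods therefore does not excuse the gap.

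**Step 4: delay.** With weekly submission, if the second successive day is day k of a 7-day reporting week, the wait is 7 − k days, that is 6 down to 0. The site can calculate MAP from the pair on receipt; the automated value follows database entry.

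**Step 5: does other text fill the gap?** The subsection Prior to Discharge points forward to the same list. The training text in 9.1.18.2 and 17.8.3 and the checklist in 17.8.4 refer to out-of-range or patient-specific values without giving a number. SAP 8.8.4.1 flags MAP above 85 in a listing, which is a reporting convention and prompts no call. None supplies a high cuff MAP action level.

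**The case against.** The case for leaving the text alone is respectable. Each group is alerted on numbers it reads directly, which suits home use, and nowhere does the protocol say that the two alerts must be equivalent. Training covers the MAP target, responses to out-of-range values and patient-specific instructions, so a subject at 125/92 may well call anyway. The missed excess is small and stays below the 110 mmHg mean pressure that defines hypertension as an adverse event in Appendix 17.9. Weekly submission is a backstop, and the sponsor's time-in-range review is another layer.

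Most of this stands, and it keeps the point at low priority. It does not remove the gap: training without a number does not replace a reporting threshold, and the plan already treats a Doppler reading above 100 as needing a call.

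Several stronger readings are tempting, and the documents do not support them.

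- *Cuff subjects have no MAP trigger at all.* Item 3 gives a low-pressure one; only the high side is open.
- *Every cuff MAP above 100 at these pulse pressures goes unreported.* It does not: 140/110 (PP 30, MAP 120) exceeds both cuff limits.
- *Cuff subjects are less protected overall.* The cuff rule also fires where a MAP rule at 100 would not: 131/62 (MAP 85.0), 131/80 (97.0) and 105/96 (99.0).
- *The cuff level ought to be 95, because the targets differ by 5.* The protocol makes that adjustment for the target and does not carry it to the alert. A level of 95 is a clinical judgement outside this point.

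**Conclusion.** The point holds as a low-priority, inexpensive safety improvement. It is not an error in the plan. Cuff readings with SBP at most 130, DBP at most 95 and pulse pressure strictly between 15 and 45 mmHg can have MAP above 100, up to 106.7, on 2 successive days without an immediate report. The consequence is a delay of 0 to 6 days before the site sees them.

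This rests on the protocol's MAP formula, on weekly submission being kept, and on comparing with the Doppler level of 100 without any offset. The documents give no pulse-pressure distribution, so the number of subjects affected cannot be estimated. A rough ceiling on the expected number using the cuff rule comes from the stated approximate 40% with a palpable pulse and the fewer than 15 enrolled reported in SAP 5.2: 0.40 × 15 = 6, so fewer than 6 expected. Since the trial stopped early, the practical value lies mainly in any later protocol that reuses this text.

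A reader might infer that survival, stroke or bleeding results are affected. Nothing in the documents supports that, and the primary analysis is untouched.

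**What to change.** Keep the systolic and diastolic triggers and add to item 1 of the After Discharge list: *or calculated cuff MAP above 100 mm Hg on 2 successive days*. Every reading in the triangle above then triggers a call, and the highest MAP that triggers nothing becomes 100.

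To avoid calculation at home, give cuff subjects a card: call if SBP + 2 × DBP exceeds 300 on 2 successive days. From DBP > (300 − SBP)/2, this means a diastolic of at least 86 at systolic 130, 88 at 125, 91 at 120 and 93 at 115. At 110 or below the existing diastolic limit of 95 already does the work. Put the same values in the diary and in the 17.8.4 checklist item on what to do when pressure is not optimal.

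The cost is one clause, small wording changes in the diary and checklist, and a one-page card. The downside is a few more calls and a lookup step for cuff subjects. Because the systolic limit stays, some subjects with a wide pulse pressure and MAP at target will still call, as they do now.

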### 9.1.6 Documentation of Concomitant Medications

Administration of antihypertensive medications (e.g., beta blockers, ACE inhibitors), angiotensin II receptor blockers, nitrates (including nitric oxide), inotropes, anticoagulants (e.g. coumadin, heparin), anti-arrhythmics, antiplatelet medications (e.g. aspirin, clopidogrel bisulfate), antibiotics and diuretics at all study visits between screening and month 24, and at Explant (where applicable) will be recorded in the eCRF.

In addition anticoagulant and antihypertensive medications will continuously be recorded throughout the study.

Information collected may include:

- Drug
- Dose
- Route of administration
- Frequency
- Start/ Stop Date

Any Concomitant Medications taken prior, up to onset and to treat an Adverse Event will be collected at the time of each event, including any specific medications pertaining to the anticoagulation guidelines for thromboembolism, stroke and/or VAD thrombosis.

**9.1.7 Echocardiogram/ qPulse™**

Parameters measured via Echocardiogram will include the following captured at screening/ pre-implant\*, and month 1, 3, 6, 12, 18, 24.

*Echocardiograms obtained within the 6 months prior to ICF may be used for screening measurements.	Unit	Screening/ Pre-implant*	Month 1, 3, 6, 12, 18, 24
qPulse setting		NA	X
Set Speed (rpm)	rpm	NA	X
Pump Flow (l/min)	l/min	NA	X
Pump Power	watt	NA	X
Aortic valve opening Y/N	Yes/ No	X	X
Aortic valve opening/min	min	X	X
Aortic valve opening duration	ms	X	X
Aortic Insufficiency	None/ Mild/ Moderate/ Severe	X	X
Commissural fusion	Yes/ No	X	X
LVEF	%	X	X
LVEDD	cm	X	X
LVESD	cm	X	X
LVEDV	ml	X	X
LVESV	ml	X	X

\* qPulse settings NA for screening

Additional Parameter to be measured :	Pre-implant, Month 1, 3, 6, 12, 18, 24
Aortic regurgitation	X
Mitral regurgitation	X
Tricuspid regurgitation	X
LA dimension(Diameter)	X
LV wall thickness	X
Presence of LV Thrombus	X

- When hemodynamically stable turn qPulse on with the MEDIUM setting
- If the aortic valve is not opening on the MEDIUM setting then consider switching to the HIGH setting
- If the aortic valve is opening every cardiac cycle and not only during the low rpm portion of the qPulse cycle then consider switching to the LOW qPulse setting.

